Once the period of time given to dyads to complete the baseline questionnaire has elapsed, IFF Research link the questionnaire return to the dyad's referral form data, pseudonymise the data and pass the data record to Manchester Metropolitan University (Man Met). A researcher based in Man Met's Policy Evaluation and Research Unit (PERU), who is blind to the identities of the dyads concerned will then randomise that dyad. Full details of the randomisation procedures are set out below. Once the dyad has been randomised, the outcome of randomisation is communicated by Man Met to IFF Research who in turn inform the Local Authority (LA) of the outcome. Following randomisation, LAs are free to commence work with dyads allocated to the intervention. It is expected that LAs will commence work with dyads very soon after randomisation so that the time between the end of the intervention and collection of post-intervention data is consistent across dyads. LAs should therefore only refer dyads for whom intervention delivery could commence immediately.

IFF Research will administer a follow-up questionnaire to all dyads (including those that did not supply a baseline questionnaire) five months following randomisation. Dyads will be given two weeks to complete the follow-up questionnaire. In large part, the follow-up questionnaire will contain the same or similar questions as the baseline questionnaire, and a similar set of procedures will be followed in order to limit attrition and missingness. IFF Research will seek a complete follow-up questionnaire from all randomised dyads, regardless of whether a dyad completed a baseline questionnaire.

At the end of the 'follow-up' fieldwork period, IFF Research will pseudonymise the follow-up questionnaire data and pass them to Manchester Met for analysis. Full details of the analysis are discussed below.

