2. Is the training perceived by VIG practitioners as adequately equipping them to deliver VIG?	

 - How prepared/ confident do VIG Practitioners feel to deliver VIG? - What support needs do VIG Practitioners have throughout the intervention? 	In-depth interviews with delivery leads, trainers and VIG Practitioners at the end of setup/implementation and at the end of delivery
3. How have social workers experienced delivery of VIG?	

 - How do VIG Practitioners describe the experience of delivering VIG? - What went well and what went less well? - Can VIG Practitioners identify any areas of improvement? 	In-depth interviews VIG Practitioners at the end of setup/ implementation and at the end of delivery
4. What difference is VIG perceived to make to parents and why?	

 - How have parents experienced VIG? - What elements of VIG did parents find most/least useful? - What difference is VIG perceived to make to parents, and why? (e.g. parents' relationship to the focal child and to other children in the family; experience of parenting; relationship to social services) - When/for who is VIG perceived to be most effective? 	In-depth interviews with parents at the end of delivery
5. What difference is VIG perceived to make to VIG Practitioners and why?	

 - What difference is VIG perceived to make for VIG practitioners, and why? (e.g. ability to support families; engage with families; engagement with their work; job satisfaction) - What social worker characteristics/factors are perceived to influence VIG delivery? 	In-depth interviews VIG Practitioners the end of delivery
6. When / for who is VIG perceived to be most effective?	

 - What parent characteristics/factors are perceived to be related to effective VIG? - What social worker characteristics/factors are perceived to influence VIG effectiveness? 	In-depth interviews with delivery leads, trainers, VIG Practitioners at the end of setup/implementation and delivery leads, trainers, VIG

Methods

Sample and Recruitment

Sample

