- **In-depth interviews with 24 families.** In order to capture the experiences of parents and their views on the outcomes achieved, we will carry out interviews with 24 parents, spread across VIG Practitioners participating in the programme, upon completion of the 3-month intervention. Parents will receive all VIG sessions in person, and the Shared Reviews will be either in person or online. This will allow for maximum parental participation in the evaluation. Interviews will last approximately 60 minutes and as a thank you for their time, parents will be offered £30, in the form of a voucher (e.g., Amazon, Paypal, Love2Shop). This will not have an impact on state benefits that parents might be receiving. To reduce barriers to participation, we will be flexible with parent fieldwork. For example, interviews may be split over two, shorter sessions. We will not request permission to access the VIG session recordings because we will not include this in the evaluation analysis.

It is unlikely we will hit saturation because the Social Workers and families are expected to be different, with different experiences, especially since the 21 practitioners come from 4 different LAs with different CSC structures and practice standards. However, we will have ongoing discussions about what we are learning and if we feel we are starting to hear the same things with nothing new emerging then we would raise this with WWCS and discuss whether to end interviews, and how best to reallocate that evaluation budget elsewhere in the evaluation.

Method	Sample size	Time point
In-depth interviews with delivery leads	4-5 respondents	Early August 2021
Focus group with trainers and supervisors	4-8 trainers and supervisors	Early August 2021
Focus groups with VIG Practitioners in each area	Total of six groups (4-6 respondents in each group)	Early August 2021
Interviews with delivery leads and all participating VIG Practitioners in local areas	20-25	November/December 2021
A focus group with supervisors over video call	4-6 respondents	November/December 2021
Observations of four group supervision sessions	5-15 participants	August – December 2021
In-depth interviews with families	24 families	May/June 2021

Analysis

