All staff participating in the IPE (including LA staff and Babies1st staff) will be provided with information upon recruitment explaining the research and how their data will be used. These documents will stress the voluntary nature of their participation. Verbal consent to participation and to recording of the interview will be collected before the interview begins.

Parents in the trial will be contacted by IFF's in-house recruitment team in order to encourage completion of the online survey and to be invited to take part in qualitative interviews. Recruiters will use an accessible information sheet to explain the purpose of the surveys and qualitative interviews to parents and the value of their participation. Recruiters will stress that participation is entirely voluntary and will not affect their dealings with their social worker or the social care system more broadly in anyway. Verbal consent to participation and to recording of the interview will be collected before the interview begins and parents will be informed that they can choose to withdraw their consent at any time.

Registration

This protocol will be published on WWCSC's website and also the [Open Science Framework \(OSF\)](#) website

Data Protection

IFF, as data controller, is registered with the Information Commissioner's Office for Data Protection under registration number Z5571698. IFF is accredited with ISO27001, the international standard for information security. We are fully compliant with GDPR and GDPR training is given to all staff members. All our storage, handling and processing of personal and sensitive data is conducted within the UK; and in line with ISO27001 (the international data security standard, with which IFF Research is accredited). All personal data is stored on our secure drive, which only the project team has access to. Data will be shared with Man Met using a password protected Excel document, transferred via IFF's secure file sharing

site. Man Met (as data processor) will keep all data secure from any unauthorised or accidental use, access, disclosure, damage, loss or destruction by using the University's Research Data Storage system.

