[name] is an evaluation and qualitative methods specialist with 10 years' experience in designing and managing complex, mixed method evaluations for government departments and VCS organisations, typically drawing on theories of change or leading collaborative development of logic models. [name] joined IFF in 2019, after 5 years at Kantar. She is a UK Evaluation Society, Market Research Society, Social Research Association member, and an advisor on the What Works for Children's Social Care Evaluation Advisory Group.

Education

- 2010 - 2011. MSc Social Psychology (London School of Economics)
- 2005 - 2010. BA Psychology (University of British Columbia)

Timeline

Please see the timeline outlined below:

	Responsibility	2021												2022						
		M a r	A p r i l	M a y	J u n e	J u l y	A u g	S e p	O c t	N o v	D e c	J a n	F e b	M a r	A p r	M a y	J u n e	J u l y	A u g	
Set-up meeting	All	■	■																	
Trial protocol and ethics application	PERU		■	■																
Parent recruitment	Babies 1st				■	■	■	■	■	■	■	■	■							
Parent baseline and randomisation	PERU				■	■	■	■	■	■	■	■	■							
VIG delivery	LAs				■	■	■	■	■	■	■	■	■	■	■	■	■	■		
Process evaluation fieldwork – W1	IFF					■														
Parent follow-up survey	IFF							■	■	■	■	■	■	■						
Process evaluation fieldwork – W2 (practitioners)	IFF					■	■	■	■	■										
Process evaluation fieldwork – W2 (parents)	IFF															■	■			
Analysis	PERU/IFF																		■	■
Report delivery	PERU/IFF																			■

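### Nothing stops up to 24 VIG-arm parents being interviewed about what VIG did for them before they complete the follow-up questionnaire that supplies the co-primary outcomes

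*Protocol*

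**What the plan says.** **The interviews.** The protocol (Implementation and Process Evaluation, Methods, stage 2 of the qualitative data collection) plans "interviews with 24 parents, spread across VIG Practitioners participating in the programme, upon completion of the 3-month intervention". Each lasts about 60 minutes and carries a £30 voucher. The sample is spread over VIG practitioners, and the topics in the IPE Design Table are about receiving VIG, so only VIG-arm parents are eligible. One topic is "What difference is VIG perceived to make to parents and why", and its examples include how the parent relates to the focal child. The same table gives the time point as "In-depth interviews with parents at the end of delivery".

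**The endpoint.** Under Impact Evaluation, Design, "IFF Research will administer a follow-up questionnaire to all dyads (including those that did not supply a baseline questionnaire) five months following randomisation". The Summary says four months. That questionnaire supplies both MORS-SF scales, which the Outcome Measures section describes as measures of the parent's relationship with the baby.

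**The contact.** Under Ethics & Participation, trial parents are contacted by IFF's "in-house recruitment team in order to encourage completion of the online survey and to be invited to take part in qualitative interviews". Under Risks, both arms are offered £5 for the surveys.

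**The order.** No section says that the questionnaire must come before the interview.

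**The concern.** The co-primary outcomes are unblinded self-reports, and the Outcome Measures section acknowledges their exposure to social desirability. An hour spent describing what VIG changed, including in the relationship that MORS-SF measures, could alter how a parent answers MORS-SF a few weeks later. The organisation holding the interview also administers the outcome questionnaire, and control parents have no equivalent contact. Any such shift would be counted as part of the treatment effect.

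The contact and the voucher could also raise follow-up response among those interviewed. The protocol already expects response to be better in the intervention arm (Missing data and imputation).

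**Working it through.** **1. Interval from the stated durations.** Delivery is expected to start promptly after randomisation (Design), so it is taken as month 0. The intervention lasts 3 months (stage 2 text) or 3 to 4 months (Interventions section). Follow-up is at 4 months (Summary) or 5 months (Design).

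| Intervention ends | Follow-up at 4 months | Follow-up at 5 months |
|---|---|---|
| 3 months | interview 1 month before | interview 2 months before |
| 4 months | same time | interview 1 month before |

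No combination places an interview at completion after the questionnaire.

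**2. Calendar.** The methods table dates the parent interviews May/June 2021, before intake opens in July or August 2021, so it cannot settle the order. Counting columns, the Timeline chart shows them in about May-June 2022 and the follow-up survey in about September 2021 to March 2022. The months may be off by one because the chart was read from extracted text.

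The follow-up bar does not fit the rest of the protocol. Intake runs to the end of March 2022 (Summary), so follow-up runs to the end of July 2022 (+4 months) or the end of August 2022 (+5 months). Within the chart itself, the follow-up bar ends one column after the randomisation bar (columns 13 and 12), where four or five are needed. That comparison does not depend on a one-column shift.

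With interviews in May-June 2022, the order depends on when the dyad was randomised:

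| Randomised | 3-month VIG ends | Follow-up due (4 or 5 months) | Interview relative to follow-up |
|---|---|---|---|
| Jul-Nov 2021 | Oct 2021-Feb 2022 | Nov 2021-Apr 2022 | after (last window closes mid-May 2022) |
| Dec 2021-Jan 2022 | Mar-Apr 2022 | Apr-Jun 2022 | mixed |
| Feb-Mar 2022 | May-Jun 2022 | Jun-Aug 2022 | before |

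Mid-May is 30 November 2021 plus five months plus two weeks. The parents who meet both the May-June window and the completion trigger are those in the last row, who would be interviewed first.

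**3. Share of the arm.** 252 / 2 = 126 randomised to VIG, and 24 / 126 = 19%. Of the 71 intervention completers in the sample-size table, at most 24 / 71 = 34%.

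**4. Size.** The yardstick is the protocol's minimum detectable effect size (MDES) of 0.44. The harmonic mean of 67, 47, 13 and 13 is 21.05, so the calculation uses 4 × 21 = 84 dyads. With 79 degrees of freedom, (1.990 + 0.846) × √(0.50 / (0.25 × 84)) = 0.438, which reproduces 0.44. With all 141 completed cases the same formula gives 0.34; the comparison below does not turn on which is used.

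The documents give no effect of an interview on later answers. Assume a shift of 0.1 to 0.3 SD in each parent interviewed first. The shift in the arm mean is the share affected times that:

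- All 24 interviewed first and all complete: 24/71 × (0.1 to 0.3) = 0.03 to 0.10 SD.
- 19% of the arm affected: 24/126 × (0.1 to 0.3) = 0.02 to 0.06 SD.
- Only dyads randomised after November 2021 affected: the Secondary Analysis section expects about 150 dyads by then, leaving 102 of 252 (40%). Sampling interviewees in proportion gives 0.40 × 24 ≈ 10, and 10/71 × (0.1 to 0.3) = 0.01 to 0.04 SD.

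The overall range is about 0.01 to 0.10 SD.

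**The case against.** A reader might infer that the protocol places the interviews before the endpoint and that a whole arm is primed and paid. The documents do not support that. The chart puts the interviews after its follow-up bar. The IPE Design Table's end of delivery reads as a programme stage, since it is paired with the end of set-up for leads, trainers and practitioners, and programme delivery closes by June 2022. A single two-month block is not rolling interviewing, and by mid-May 2022 about half of 150, or 75 VIG dyads, would be past follow-up, three times the 24 needed. At most 24 of about 126 are interviewed, and the £5 survey payment goes to both arms; only the £30 is one-sided. All this stands. It makes the order unfixed. It does not make it safe, because the follow-up bar is too short and the completion trigger picks out late-randomised dyads.

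The direction is also uncertain. The interview asks what was least useful as well as most useful, and every VIG parent already goes through repeated guided reflection and a closing review session. The added effect of one interview is therefore undemonstrated, which is why the size is given only as a range under an assumption.

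On response, the plan is better protected. It anticipates differential follow-up and provides imputation by arm, a drop-out model as fallback, and extreme bounds. These address missing outcomes. They do nothing about changed answers among parents who respond.

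**Conclusion.** The point holds as an unfixed order with inconsistent dates. The stage 2 wording, read literally, puts the interview 0 to 2 months before the co-primary measurement, no rule prevents this, and the calendar does not resolve it. Dyads randomised by November 2021 would be safe with interviews from mid-May 2022; those randomised in about February-March 2022 would be interviewed first.

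The likely effect is small: about 0.01 to 0.10 SD on the VIG arm mean, so at most just under a quarter of the 0.44 MDES (0.10 / 0.44 = 23%). That rests on the assumed 0.1 to 0.3 SD shift, and the upper end needs all 24 to be interviewed first and to complete both waves. This is a cheap improvement to an otherwise workable interview plan. It does not threaten the trial, and no sample-size figure changes.

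**What to change.** In the stage 2 text, the IPE Design Table and the methods table, state that a parent is interviewed only after that dyad's follow-up questionnaire has been returned or its two-week window has closed, and draw the 24 interviewees from such dyads. Instruct IFF's recruitment team not to raise the interview or its £30 voucher before that point. Reconcile the follow-up timing (Summary, Design, Timeline) and the interview dates (stage 2 text, methods table, Timeline). The rule works whichever follow-up interval is confirmed.

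The cost is one sentence and a filter on the sampling list, with no added interviews or budget. There are two downsides. Recall is somewhat longer than with an interview at completion: for a dyad randomised in November 2021 that finishes in February or March 2022, a May-June interview comes about two to four months after the end. Interviewees would also come mainly from dyads randomised earlier, which the report should state.

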The Video Interaction Guidance (VIG) programme is being implemented between March 2021 (with intake from July 2021) and June 2022 in four English Local Authorities (LAs). VIG is a relationship based parenting intervention in which a VIG practitioner films a parent and child interacting in short, one-to-one sessions. By providing feedback on these sessions based on edited clips of better than usual moments, VIG aims to promote parental sensitivity, child attachment and longer term social and emotional development.

The intervention developer, Babies 1st, will train and supervise 21 VIG Practitioners across the four LAs. Practitioners will undertake the role in addition to their substantive role (e.g. social or family worker) and will each work with a minimum of six families (typically a focal parent and infant dyad) over eight sessions or more.

The programme is being evaluated by IFF Research and the Policy Evaluation and Research Unit (PERU) at Manchester Metropolitan University (Man Met). The evaluation comprises impact, implementation (process) and cost components. The impact study design is a pragmatic, multi-site, effectiveness trial, with individual family dyads allocated to intervention and control within sites, at random, on a 1:1 intervention to control basis. Families allocated to the intervention group will receive VIG in addition to their usual care; those in the control group will receive usual care only. All families will be asked to complete a baseline questionnaire containing psychometric measures prior to randomisation and also at four months post-randomisation. In addition, LAs will supply child protection outcomes from administrative data six months post-randomisation.

Intake will begin in August 2021 and will continue until the end of March 2022. Randomisation will begin in July 2021, and the intervention for all families will end by June 2022. An evaluation report will be published by the end of August 2022.

The evaluation includes a review point (September 2021) to allow for changes to the protocol and evaluation activity on account of factors which are currently unknown (e.g., the amount of dropout and proportion of parents requiring translation services or additional support to complete the survey). For further details see p.12.

Table of Contents

Background and Problem Statement	6
Intervention and Theory of Change	6
Logic Model	9
Interventions	10
Mechanisms	10
Outcomes	10
Impact Evaluation	11
Research Questions	11
Design	12

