Once referral and consent procedures are complete, details of each dyad are passed to IFF Research, who check the completeness of the referral form data and confirm eligibility (that the dyad meets the study inclusion criteria). Subsequently, IFF administer a baseline questionnaire to the focal parent. The baseline questionnaire contains the following measures, details of which can be found in Appendix A: MORS-SF, Karitane Parenting Confidence Scale, Parental Stress Scale. For the sample randomised between July and November 2021, child protection outcomes (CiN, CPP, CLA and initiation of pre-proceedings) are collected from administrative case data held by the local authorities and further details provided later in this section. Full details of the measures included within the baseline questionnaire, along with the justification for their choice, and the reliance on self-completion questions rather than observations, is provided in the section entitled 'Outcome measures' below.

The respondent (focal parent) is expected to be the focal child's mother but may be the father where he is the only, or primary, care giver. Dyads are given two weeks to complete the questionnaire. It is important to note, that the study's funders have decided that all dyads that meet the study inclusion criteria and who provide their consent should be randomised, regardless of whether a complete baseline questionnaire is received. This means that some missing data, either item or unit (dyad) missing, can be expected at baseline. The evaluators in partnership with Babies 1st and the study sites will take a number of steps to limit non-response or missingness at baseline, such as telephone reminders to non-respondents, telephone support for focal parents to complete the questionnaire, and support for social workers and VIG Practitioners to support and encourage parents to participate.

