In principle, because baseline data are collected prior to randomisation, missingness will not lead to bias in estimates of AITT (Sullivan et al., 2018)¹⁷. Completed cases analysis where baseline observations are missing is unlikely to cause bias but would lead to a diminished sample size. The same is not likely to be the case where observations are missing at follow-up. It seems highly probable that follow-up missing data processes will differ in the trial arms; for example, it seems possible that follow-up interviews will more likely be obtained from those assigned to the intervention. Given that we anticipate missing data at both baseline and follow-up for the primary outcomes derived from the MORS-SF instrument, we are faced with two potentially different missing data processes acting to generate the achieved sample simultaneously. In the case of follow-up data, missing data processes are most likely to be experimentally MAR or MNAR. For the baseline, missingness is uncorrelated with randomisation in expectations due to the fact that baseline measures are collected prior to randomisation.

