
Specific risks (although minor) may arise due to the nature of the survey and interview questions. The surveys will contain multiple measures of a psychological and development nature (e.g., stress, confidence, parenting ability). Responding to statements included in these measures may potentially alert parents to their behaviours and beliefs, and as a result may cause them some concerns.
	
At the end of the surveys parents will be instructed to speak to their case working social worker or VIG practitioner in the first instance if they have any concerns about the questions to which they responded, either in the surveys or in the interviews.
 
Dyads assigned to the intervention or control groups will both receive the usual LA-specific support provided to infants who are on a Child Protection or Child in Need plan, and their parents. Given that all these families will be open to children's social care, they will all have a social worker and be receiving this support.
 
The VIG practitioners involved are awarded a national recognized accreditation, proving they have reached the desired skills level. The training and supervision they receive is delivered by highly experienced VIG trainers. They have delivered similar training in many and various projects over the last 10 years, including in mother baby units, the NSPCC, CAMHS, Children's Services, Family Drug and Alcohol Courts, and Family Assessment units. Hence, practitioners will have the expertise to mitigate psychological risk or discomfort that may arise during the intervention.

Parents struggle to complete the online survey due to literacy issues, issues with understanding the survey measurements, or lack of access to internet
	
Telephone reminders will be carried out to non-responders and as part of this call interviewers will offer support in order for parents to complete the survey. Social workers and VIG practitioners will also be provided with a copy of the survey and information about how to support and encourage parents to participate.

Parents struggle to complete the online survey due to lack of English comprehension
	
Social workers are asked to confirm that the focal parent is sufficiently fluent in English to take part in the surveys.

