
Low response to the online surveys
	
Telephone reminders will be carried out to all non-responders. Social workers and VIG practitioners will be provided with information about the survey and asked to encourage parents to participate.
 
All parents in the trial will be invited to complete the follow-up survey, including those who do not respond to the baseline survey.
 
Parents in both the intervention and control groups will be offered a financial incentive of £5 to complete both the baseline and follow up surveys.

Low response to qualitative interviews
	
Social workers, delivery leads and trainers will be recruited with support from nominated leads for the intervention in each LA, as well as Babiest1st. Staff will be provided with accessible information about the IPE and why their participation is needed. Staff who are unable to participate during group sessions or site visits will be offered a one-to-one interview by telephone or video call at a time convenient to them.

	Interviews with parents will similarly be offered at a time which suits them and parents will be given a financial incentive of £30 as a thank you for their time.
Recruitment will be managed by each participating local authority and there is therefore a risk that areas do not take a consistent approach to recruitment and engage slightly different cohorts of parents.	Areas have been asked to appoint a recruitment lead to confirm eligibility before submitting recruited parents to IFF for randomisation and each lead will be provided with guidance materials on eligibility. Any notable differences between cohorts will be analysed upon completion of the baseline survey.
There remains considerable uncertainty about how the Covid-19 pandemic will play out over the delivery period.	This means we will need to be understanding and flexible in our dealings with Babies 1 st and with participating local authorities (LAs). This may mean needing to adapt our fieldwork approach and timings for process evaluation and we are happy to do this

Ethics & Participation

WWCSC's Research Ethics Committee have given ethical approval

Mat Met also submitted a separate ethics application (no. 33599) to the University's Arts and Humanities ethics committee in respect of their role as data processors. This was approved on 21/05/2021.

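### VIG practitioners may prompt and help parents with the follow-up questionnaire, an extra channel that serves the intervention arm and risks biasing the self-reported outcomes

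*Protocol*

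**What the plan says.** The Risks section deals with survey completion in two rows. The row on parents who struggle with literacy, with understanding the measures or with internet access says that "Social workers and VIG practitioners will also be provided with a copy of the survey and information about how to support and encourage parents" to take part. The row on low response says "Social workers and VIG practitioners will be provided with information about the survey and asked to encourage parents to participate". Neither row separates baseline from follow-up.

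The Design section lists the same step at baseline, as "support for social workers and VIG Practitioners to support and encourage parents to participate". Of the follow-up questionnaire it says that "a similar set of procedures will be followed in order to limit attrition and missingness".

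On contact by arm, the Summary says that "those in the control group will receive usual care only". The Risks section says of families in both arms that "they will all have a social worker and be receiving this support". Telephone reminders and the £5 incentive are also offered to both arms.

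Under Missing data and imputation the protocol expects response to differ: "it seems possible that follow-up interviews will more likely be obtained from those assigned to the intervention". It does not connect this with the practitioners' role in the survey.

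**The concern.** Baseline questionnaires are completed before randomisation, so practitioner support cannot differ by arm at that point. The follow-up questionnaire comes after allocation, and the Design section has the local authority told the result. From then on the VIG practitioner is a channel that the intervention arm has in addition to everything the control arm has.

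Both co-primaries (MORS-SF warmth and invasion) and two of the three secondaries (Karitane scale, Parental Stress Scale) are unblinded parent self-report, and Outcome Measures concedes social desirability. The MORS-SF items ask how the baby behaves towards the parent, which is the relationship that the practitioner has just been working on. If the practitioner also holds the survey and supports the parent with it, two things could move the comparison without any true effect: answers coloured by the practitioner's involvement, and a different mix of responders in that arm.

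**Working it through.** **Does the practitioner's role extend to follow-up, and does it differ by arm?**

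1. The Risks rows concern the online surveys in general, and the Design section repeats similar procedures at follow-up. Nothing confines practitioners to baseline.
2. Interventions puts delivery at 3 to 4 months. Follow-up is at four months in the Summary and five months in Design. The working relationship is therefore current or recently ended when the questionnaire goes out.
3. Social workers, IFF calls and the incentive reach both arms. What is specific to the intervention arm is the added VIG practitioner.

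**What the planned analyses cover.** The main analysis uses completed cases. For the co-primaries, multiple imputation (run separately by arm) and extreme bounds then test sensitivity to missing values. The Karitane and Parental Stress analyses use completed cases only. Imputation and bounds fill in absent values and cannot correct a returned answer that was influenced.

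**The plan's own figure.** Inputs from the sample size section and Table 3: two-sided alpha 0.05, power 80%, R² 0.50 (from 0.70² = 0.49), four sites with 67, 47, 13 and 13 complete cases, 1:1 allocation.

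- Harmonic mean site size = 4 / (1/67 + 1/47 + 1/13 + 1/13) = 21.05, so effective N = 4 × 21 = 84.
- SE = √[(1 − 0.50) / (0.25 × 84)] = 0.154 SD.
- MDES = (t0.975 + t0.80 on 78 df) × 0.154 = 0.438, which agrees with the stated 0.44.
- With all 141 complete cases, SE = √[0.50 / (0.25 × 141)] = 0.119 SD.

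**Illustration of influenced answers.** Assume no true effect and an average shift of b SD in intervention-arm answers. The chance of a significant result is 1 − Φ(1.96 − b/SE) + Φ(−1.96 − b/SE). For b = 0.10 and SE = 0.119, b/SE = 0.84, which gives 0.134.

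| Assumed shift b (SD) | 141 complete cases | Effective 84 |
|---|---|---|
| 0 | 5% | 5% |
| 0.05 | 7% | 6% |
| 0.10 | 13% | 10% |
| 0.15 | 24% | 16% |
| 0.20 | 39% | 25% |

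**Illustration of differential response.** Table 3 implies (141 + 25)/252 = 66% follow-up overall, and the planned 71 and 70 complete cases assume no difference by arm. Let response and outcome have a latent correlation ρ. The mean among responders at response rate r is then shifted by ρ·φ(Φ⁻¹(r))/r, and the bias is the difference between arms. With ρ from 0.2 to 0.4 (assumed):

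- 71% v 61%: 0.03 to 0.06 SD.
- 76% v 56%: 0.06 to 0.12 SD.

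In this model the bias runs against the intervention if better-off parents are the likelier responders, and the other way if worse-off parents are. The sign is not fixed.

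**The case against.** A reader might infer that help with the questionnaire exists in one arm only. The documents do not support that. Both Risks rows name social workers alongside VIG practitioners, every family has a social worker, and IFF calls and the incentive reach both arms. Even the confinement of the practitioner channel to the intervention arm is inferred from the design: practitioners keep a substantive social or family worker role, and the protocol does not say whether one may also be a control family's worker.

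A reader might also infer that the practitioner sits with the parent while items are scored. The text speaks of supporting and encouraging participation. Because the row concerns literacy and understanding of the measures, help with items is a fair reading, but it is not stated. On the five-month schedule sessions would normally be over.

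Nor does the protocol simply impute the response problem away. It analyses completed cases first, treats imputation as a sensitivity check, and adds bounds that make no assumption about the missingness. It also accepts self-report knowingly, as a trade-off.

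Finally, it is tempting to add the two biases into one figure. With 80% v 60% response and the extra responders 0.5 SD different (both assumed), the response bias is 0.20/0.80 × 0.5 = 0.125 SD. Adding an assumed 0.1 SD answer shift gives 0.225 SD, or 51% of the stated MDES of 0.44. That sum gives both parts the same sign without evidence and ignores the baseline covariate. If the 0.5 SD difference were already present at baseline, a slope of 0.7 would leave 0.5 − 0.35 = 0.15 SD, and the response part falls to 0.25 × 0.15 = about 0.04 SD.

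These points limit the claim. They do not remove it: nothing excludes practitioners from follow-up support, and no planned analysis deals with influenced answers.

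**Conclusion.** The point holds as a risk of bias, not as a demonstrated bias. It rests on one additional post-randomisation channel, the VIG practitioner, which by design serves intervention families. The stronger limb is influence on answers, because the protocol has no analysis for it. Differential response is the weaker limb: its direction is unknown, and it is partly probed for the co-primaries, though not for the Karitane and Parental Stress scales.

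The documents give no size. Under the stated assumptions (no true effect, R² 0.50), an answer shift of 0.10 to 0.20 SD would raise the false-positive chance to about 13% to 39% with 141 complete cases, or 10% to 25% with the effective 84. The shift itself is assumed, so these figures show only that a modest one would matter. They do not support saying that the procedure would account for any given share of the detectable effect.

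**What to change.** Amend the follow-up paragraph in Design and the two survey rows in Risks so that, for the follow-up questionnaire:

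- nobody acting as a VIG practitioner prompts parents or helps with completion;
- all help with items comes from IFF telephone interviewers, on the same contact schedule in both arms and unaware of allocation where possible;
- any reminder from the local authority is the same neutral prompt in both arms, with no help on items, so that social workers are treated alike and no reverse asymmetry arises where the practitioner is also the family's own worker;
- mode of completion and any assistance are recorded for each return.

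Practitioner support at baseline may stay, since it precedes randomisation. The change uses the telephone support already planned and removes a task from practitioners. The cost is possibly a slightly lower follow-up response, mainly in the intervention arm.
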